6.3 INVESTIGATIONAL PRODUCT STORAGE

Study drug will be shipped at 2°C to 8°C (refrigerated [36°F to 46°F]) to the investigator's site. Upon receipt at the site, the responsible site staff or pharmacist should verify the integrity of the vials. Study drug should be stored at 2°C to 8°C (refrigerated [36°F to 46°F]). The contents of the vial should appear as a clear to opalescent, colorless to yellow solution; fine translucent particles may be present. This is normal.

The investigator must maintain an accurate record of the shipment, storage, and dispensing of the study drug in a drug accountability log. An accurate record including the date and amount of study drug dispensed to each subject must be available for inspection at any time. A study CRA assigned to monitor the investigational site will review these documents once study drug has been received by the investigational site. Study drug will be accounted for on an ongoing basis during the study.

6.4 INVESTIGATIONAL PRODUCT ADMINISTRATION

Guidelines for dose preparation can be found in the pharmacy manual.

PRO 140 will be provided to the administering personnel in single-use syringes prepared from vials of study drug stored at 2-8°C at the site pharmacy prior to use. Each of two syringes is filled to deliver 1.0 mL of study drug.

Equivalent volumes of study drug will be administered subcutaneously on opposite sides of the abdomen.

A 25-gauge needle should be used to remove IP from vial and for administration to subjects.

IP should be administered slowly over 15 seconds per mL. IP should not be kept in syringe for longer than 60 minutes.

Note: Patients with low body fat percentages may find subcutaneous injections uncomfortable. In such cases, PRO 140 700 mg can be injected as four 175mg/ml injections of 1 mL each and/or can be placed at different areas other than abdomen as per discretion of the Investigator.

Following each SC delivery of drug, careful examination will be made to assess the appearance of any study drug Injection Site Reactions (ISRs) as described in [Section 16.3](#).

All doses of study drug will be prepared by either the credentialed pharmacist or qualified medical professional and will be administered as SC injection by a qualified medical professional

(MD, DO, PA, LPN, LVN, NP, RN, or CMA if permitted by state law) or self-administered by subjects depending on the study visit week.

Note: It is preferred that the same injection site be used throughout the study. At the same time, it is not recommended to inject the study drug into areas where skin shows signs of a previous injection site reaction. It is advised to change the injection site if any previous injection site reaction remains unresolved.

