4 STUDY SCHEDULE

As shown in [Figure 4-1](#), this study is divided into three phases: Screening, Treatment and Follow-up.

Figure 4-1: Study Schematic

(1) **Screening Phase:** This phase lasts up to 6 weeks, consists of Screening Visit (SV) and begins with signing of Informed Consent. Assessments performed during this phase determine the subject's final eligibility for study participation. First treatment will be administered within 42 days of Screening Visit.

All subjects will continue taking their existing ART (failed regimen) during the Screening Phase and first week of the Treatment Phase (Part 1).

(2) **Baseline:** The Baseline (T0) visit will take place within 6 weeks of the Screening Visit, as soon as HIV-1 viral tropism, genotypic and/or phenotypic resistance results are available for review by Investigator. HIV RNA and TruCount Assay will be performed to ensure continued eligibility prior to the first Treatment Visit (T1).

(3) **Treatment Phase:** Subjects will receive up to 25 treatments, given approximately every week (window period of ± 3 days) or until treatment failure is experienced, whichever comes first.

The first Treatment Visit (T1) will take place within one week of the T0 visit.

The injectable study treatment (PRO 140) will be administered by a qualified medical

professional (MD, DO, PA, LPN, LVN, NP, RN, or CMA if permitted by state law) or self-administered by subjects.

Note: *Study treatment injections at T1, T2, T3, T7, T11, T15, T19 and T23 must be administered at clinic. The remaining study treatment injections may be self-administered by subjects outside the clinic.*

Any time during Treatment Period Part 2, if treatment failure occurs, Investigator will readjust antiretroviral regimen based on HIV-1 genotypic and/or phenotypic drug resistance results obtained during the TF visit.

Subjects will be allowed to continue PRO 140 with existing OBT regimen while waiting for new regimen to be constructed by the Investigator.

Treatment failure is defined in terms of virologic non-response and virologic rebound in Part 2 of the Treatment Phase of the study:

a) Virologic non-response is defined as two consecutive viral load results of:

- $<0.5 \log_{10}$ copies/mL decrease in HIV-1 RNA at Day 7 of Treatment Period Part 2. *[Assessment Timepoint: T3 visit]*

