- [5] The neurological assessment tool is based on the three question survey used by Simioni et al. (Simioni S, 2010) Additional neurological assessment modalities may be used as per Investigator's discretion.
- [6] Post treatment vital signs will be recorded at T1-3, T7, T11, T15, T19, T23, EOT and TF visits (i.e., blood pressure, heart rate, respiration rate, and temperature)
- [7] Hemoglobin, Hematocrit (HCT), Red Blood Cells (RBC), White Blood Cells (WBC) with total and differential count, Absolute Neutrophil Count (ANC) and platelets.
- [8] Serum Biochemistry
 - Hepatic function indicators: total and direct bilirubin, alkaline phosphatase, aspartate aminotransferase (AST), alanine aminotransferase (ALT), total protein, Lactate dehydrogenase (LDH)
 - Renal function indicators: BUN, creatinine
 - Electrolytes: sodium, potassium, chloride, calcium and bicarbonate
 - Other: glucose (random), cholesterol (total)
- [9] Prothrombin time (PT) and International Normalized Ratio (INR)
- [10] ONLY performed on women of childbearing potential.
- [11] Urine samples will be tested for color, appearance, specific gravity, pH, protein, glucose, occult blood, ketones, leukocyte esterase, nitrite, bilirubin, urobilinogen, and microscopic examination of urine sediment.
- [12] Includes: CD3 %, CD4 %, CD8 %, Absolute Lymphocytes, CD3 cell count, CD4 cell count, and CD8 cell count
- [13] PK samples for PRO 140 will be collected prior to IP administration at the T1, T7, T15, EOT and TF visits.
- [14] Serum conc. of ART Drugs prior to IP administration at the T1, T7, T15, EOT and TF visits.
- [15] Injection Site Reaction Assessment as assessed by Investigator (or designee) at each treatment visit that occurs in the clinic.
- [16] Subject-perceived injection site pain (average pain since last treatment) will be assessed using the Pain Visual Analog Scale (VAS) prior to each study treatment administration that occurs in the clinic.
- [17] Monogram Biosciences Trofile® DNA and RNA
- [18] Monogram Biosciences PhenoSense® GT and Gensosure Archive (and PhenoSense Integrase and GeneSeq Integrase testing, if applicable)
- [19] Monogram Biosciences HIV-1 PhenoSense® Entry assay with AMD3100 (CXCR4 inhibitor drug), Maraviroc and PRO 140 (CCR5 inhibitor drugs).
- [20] Quest Diagnostics HIV-1 Coreceptor Tropism with Reflex to Ultradeep Sequencing and/or HIV-1 Proviral Tropism

Table 4-2: Schedule of Assessments –Follow-Up (FU) Phase

(a) Subjects who do NOT experience treatment failure

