4.3.3 End of Treatment (EOT) Visit

The following assessments will be performed for subjects who do not experience treatment failure at any time during the Treatment Phase:

- Assess for any Adverse Events and changes in Concomitant medications (see [section 9](#) and [7.5](#)),
- Complete Physical Examination (see [section 7.7](#)),
- Vital Signs (see [section 7.10](#)),
- Neurological Assessment (see [section 7.9](#)),
- Subject-perceived Injection Site Pain Assessment (see [section 7.14](#)),
- Collection of Blood Specimens (see [section 7.11](#)) for
 - Plasma HIV-1 RNA level
 - TruCount T Assay
 - Complete Blood Count
 - Biochemistry
 - Anti-idiotypic antibodies to PRO 140
 - PK sample for PRO 140
 - Serum Conc. of ART Drugs

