7.13 INJECTION SITE REACTION ASSESSMENT

At each treatment visit that occurs at the clinical site, an injection site reaction assessment will be made for the current and previous injection sites. Injection site reaction assessments are recorded by the Investigator (or designee) starting after the first injection is given. Refer to [sections 9.1.8](#) and [16.3](#) for more details.

[figure not shown]

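### Section 6.4's rules on preparing doses and examining the injection site do not provide for the up to 17 of 25 doses that subjects may self-inject outside the clinic

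*Protocol*

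**What the plan says.** **Preparation.** Section 6.4 says "All doses of study drug will be prepared by either the credentialed pharmacist or qualified medical professional". The same sentence then allows administration by a professional or by the subject, so it opens administration to subjects but not preparation. The section also says "PRO 140 will be provided to the administering personnel in single-use syringes prepared from vials of study drug" kept refrigerated at the site pharmacy, and that "IP should not be kept in syringe for longer than 60 minutes".

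**Place of dosing.** Sections 4 and 4.3 require T1, T2, T3, T7, T11, T15, T19 and T23 to be given at the clinic. For the others, section 4 says "The remaining study treatment injections may be self-administered by subjects outside the clinic".

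**Injection site examination.** Section 6.4 says "Following each SC delivery of drug, careful examination will be made" to look for reactions. Section 7.13 says that at each treatment visit at the clinical site "an injection site reaction assessment will be made for the current and previous injection sites". Footnote 15 to Table 4-1 agrees: "Injection Site Reaction Assessment as assessed by Investigator (or designee) at each treatment visit that occurs in the clinic". The end-of-treatment (EOT) list in section 4.3.3 includes a complete physical examination and the "Subject-perceived Injection Site Pain Assessment", but no investigator assessment of reactions.

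**The concern.** Two rules in section 6.4 are written for every dose, but they suit only doses given where staff are present.

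On preparation, a site that hands out vials for the subject to fill breaks the staff-only rule. A site that hands out filled syringes is bound by the 60 minutes, which does not suit a dose taken days later. A professional preparing the dose at the place of injection would comply, but the protocol makes no arrangement for this.

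On examination, investigator evaluation of injection site reactions is a stated safety measure (section 8.2.3), and section 9.1.8 makes these reactions adverse events of special interest. Section 16.3 grades bleeding that stops by itself and leakage by how it responds to the injection rate. An investigator cannot see either one weeks later. Section 9.1.8 also requires permanent discontinuation if the same Grade 3 event recurs at the next administration, yet up to three outside doses in a row can pass before an investigator examines the sites.

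**Working it through.** **1. Number of doses.** Inputs are from sections 4 and 4.3.
- Total: 1 (T1) + 24 (T2 to T25) = 25, which reproduces the protocol's figure of up to 25.
- Clinic doses: T1, T2, T3, T7, T11, T15, T19, T23 = 8.
- May be taken outside: 25 − 8 = 17, and 17/25 = 68%. By run: T4–6, T8–10, T12–14, T16–18, T20–22, T24–25 = 3 + 3 + 3 + 3 + 3 + 2 = 17.

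**2. Delay to the first reaction assessment if all 17 are taken outside.** The next clinic treatment visits are T7, T11, T15, T19 and T23.
- About 1 week: T6, T10, T14, T18, T22 (5 doses).
- About 2 weeks: T5, T9, T13, T17, T21 (5 doses).
- About 3 weeks: T4, T8, T12, T16, T20 (5 doses).
- No later clinic treatment visit: T24 and T25 (2 doses). Check: 5 + 5 + 5 + 2 = 17.

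If Table 4-1 places a reaction assessment at EOT, and EOT is assumed to fall one week after T25, then T25 joins the first group and T24 the second: 6 + 6 + 5 = 17. Each weekly step has a ±3-day window (4 to 10 days), so three steps could span 3 × 4 = 12 to 3 × 10 = 30 days.

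**3. Rules side by side for an outside dose.**
- Who prepares: section 6.4 says staff, for all doses. Section 6.5 foresees dispensing to a subject and recording the preparer, but nothing makes the subject a permitted preparer.
- When injected: within 60 minutes of filling. No text links this to a dose taken outside.
- When examined: section 6.4 says after each delivery; section 7.13 and footnote 15 say at clinic treatment visits, with previous sites included.

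**4. Volumes a subject would be given if asked to prepare.** Inputs are from section 6.1.
- Dose intended: 2 injections × 2 mL × 175 mg/mL = 700 mg, as stated.
- Drawn as instructed: 2 vials × 1.0 mL × 175 mg/mL = 350 mg.
- Both vials emptied: 2 × 1.4 mL × 175 mg/mL = 490 mg.
- Needed: 700/175 = 4 mL, or four vials at 1 mL each.

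The shortfall applies equally to clinic doses. It matters here because letting subjects prepare doses would pass the wrong instruction on to them.

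**The case against.** The strongest reply on examination is that the operative rule already exists. Section 6.4 names no examiner, time or place, while section 7.13 and footnote 15 are specific and cover previous sites. Adverse events are also elicited by direct questioning (section 9.1), pain is scored on the visual analogue scale, and the EOT visit has a complete physical examination that includes dermatologic findings. Some section 16.3 signs, such as ulceration or necrosis, can persist to a later visit. Most of this stands: outside doses get a deferred look and reactions remain reportable. It does not fully answer the point, because the pain scale looks back only over the past week or since the last treatment, and brief bleeding or leakage still rests on recall.

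On preparation, it can be said that outside dosing is optional, that the syringe limit is worded as advice, that a qualified professional need not be site staff, and that preparation details belong to a pharmacy manual not shown here. The first three are fair. The manual could not override a protocol sentence covering all doses.

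Two stronger readings are tempting. A reader might infer that the protocol makes outside dosing impossible. It does not: a professional could prepare the dose on the spot. A reader might also infer that reactions after T24 and T25 are never assessed. That rests only on the section 4.3.3 list. The reaction row of Table 4-1 cannot be aligned reliably in the extracted text, but it carries the same run of marks as the pain and adverse-event rows, both of which section 4.3.3 lists at EOT. The row may therefore reach EOT too.

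**Conclusion.** The point holds. The preparation half is the firmer one: section 6.4 sets rules for all doses, sections 4 and 4.3 permit up to 17 of 25 (68%) to be self-injected outside the clinic, and the protocol provides no route that reconciles them. The examination half is smaller. The sections disagree on timing, the workable rule leaves a delay of about 1 to 3 weeks, and section 4.3.3 should say plainly whether reactions are assessed at EOT.

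The figures are ceilings for a subject who receives all 25 doses and uses the option every time; actual use may be anywhere from 0 to 17. The number of reactions missed cannot be computed from the protocol. The documents do not support reading this as a threat to the primary result, because the one-week endpoint rests on the T1 dose, which must be given at the clinic. Nor do they show what dose anyone actually received; the 350 mg figure describes the written instruction only.

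**What to change.** 1. **Preparation (6.4).** Permit trained subjects to prepare outside doses from dispensed vials kept at 2–8°C and to inject within 60 minutes of filling. Alternatively, limit outside doses to those that a professional prepares on the spot. Record who prepared each outside dose.
2. **Volumes, for all doses.** Correct the two-vial, 1 mL-per-vial instruction in section 6.1, the two 1 mL injections in section 4.3.1, the 1.0 mL syringe fill in section 6.4, and the kit and syringe labels in section 6.2, so that they agree with 700 mg.
3. **Examination.** In section 6.4, limit the immediate examination to in-clinic doses. Have subjects note the section 16.3 signs they can observe after each outside dose, and have section 7.13 call for review of that record at the next clinic visit.
4. **EOT.** List a reaction assessment in section 4.3.3, consistent with Table 4-1.

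The cost is wording in sections 6.4, 7.13 and 4.3.3, a short subject record and a preparer entry. If subjects prepare doses, a training checklist is also needed. The corrected kit contents, labels and draw volumes are needed whichever route is chosen. A table of reactions by place of injection would be a reasonable option for the SAP, but the point does not depend on it.

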6.5 INVESTIGATIONAL PRODUCT RECEIPT AND ACCOUNTABILITY

Study drug must be used in accordance with this protocol and only under the direction of the responsible investigator. The investigational site must maintain complete and accurate records showing receipt and disposition of all study drug, including master records listing the date of receipt, the number and nature of medication units received, and a dispensing record which includes each quantity dispensed, identification of the staff member/subject to whom dispensed, the date of dispensing, the intended study participant, and the identification of the preparer. All used and unused study kits will be retained by the investigational site until drug accountability can be confirmed by study CRA during the monitoring visits. Instructions will be provided by Sponsor regarding final disposition of all study drug in compliance with applicable regulations.

6.6 INVESTIGATIONAL PRODUCT DISPOSITION

All drug supplies are to be used only for this protocol and not for any other purpose. The investigator must not destroy any drug labels or any partially used or unused drug supply until instructed by the Sponsor. At the conclusion of the study and as appropriate during the course of the study, the investigator will return all used and unused drug containers and drug labels to the drug distributor as directed by the Sponsor. A copy of the completed drug disposition form will be sent to CytoDyn, Inc. or to its designee.

7 DESCRIPTION OF PROTOCOL ASSESSMENTS AND PROCEDURES

7.1 INFORMED CONSENT

Written informed consent will be obtained for this study by the Investigator or designee from all subjects before the performance of any protocol-specific procedure. This study will be conducted in accordance with the provisions of the Declaration of Helsinki.

In obtaining and documenting informed consent, the Investigator must comply with applicable regulatory requirements and must adhere to Good Clinical Practice (GCP). The Investigator, or designee, must fully inform subjects of all pertinent aspects of the study. Before informed consent may be obtained, the Investigator, or a person designated by the Investigator, must provide the subject ample time and opportunity to inquire about details of the study and to decide whether or not to participate in the trial. All questions about the trial must be answered to the satisfaction of the subject. Prior to the subject's participation in the trial, the written informed consent must be signed and personally dated by the subject and by the person who conducted the informed consent discussion. Authorization for release of protected health information must also be obtained, as per local policies.

7.2 ASSESSMENT OF ELIGIBILITY

During the Screening Phase and at T1 Visit (prior to treatment administration), the Investigator must assess a subject's continued suitability and eligibility for the trial. The Inclusion and Exclusion criteria of this Protocol are described in [Sections 3.3.1](#) and [3.3.2](#). If the subject is not suitable or eligible for the trial then the subject will be a screen failure.

7.3 DEMOGRAPHIC INFORMATION

For the purposes of this study, demographic information will include:

- Dates of ICF signature
- Date of birth
- Gender
- Race (American Indian/Alaskan Native, Asian, Black/African American, Native Hawaiian/Pacific Islander, Caucasian, or other)
- Ethnicity (Hispanic/Latino or Not Hispanic/Latino)

7.4 MEDICAL HISTORY

A medical history will be recorded during the Screening Phase and will include:

- All ongoing medical conditions
- Disease history (HIV), history of substance abuse, social history, blood transfusion history and any past surgeries
- All previously resolved medical conditions related to HIV or which are relevant in the judgment of the Investigator
- Any prior medical conditions that have resolved within the last year

Events that emerge prior to the first treatment (T1) will be recorded in the medical history and not as AEs. Aside from being used to determine subject eligibility, this information will permit the Investigator to record the nature, duration and severity of any ongoing baseline medical conditions prior to the patient's receiving investigational product (IP) treatment.

Medical histories will be recorded using the body system categories outlined below:

- | | |
|--------------------|-----------------|
| • Cardiovascular | • Lymphatic |
| • Respiratory | • Hematologic |
| • Gastrointestinal | • Immunologic |
| • Renal | • Dermatologic |
| • Hepatic | • Psychiatric |
| • Neurological | • Genitourinary |
| • Endocrine | • Other |

For each relevant history, the following will be documented:

- Disease/disorder/condition
- Date of diagnosis
- History status (resolved or ongoing)

7.5 HIV HISTORY

A detailed HIV history will be recorded during the Screening Phase and will include:

- Date of diagnosis
- Most recent viral load and CD4 count
- Nadir CD4 and peak viral load, if known
- ART-related history

- Current and previous ART regimens
- Date of initiation of ART
- Reasons for changes in ART
- Previous adverse drug reactions, including hypersensitivity reactions to prior therapies
- Challenges with adherence to therapy
- History of drug resistance, if known
- Opportunistic infections, malignancies, and previous adverse reactions to drugs used for opportunistic infections prophylaxis

7.6 PRIOR / CONCOMITANT MEDICATIONS AND NON-STUDY TREATMENTS

A complete history of antiretroviral therapies will be recorded in the source documents and on the appropriate page of the eCRF.

In addition to this, all other medications and therapies administered or taken by the subject beginning 30 days prior to first Screening Visit and throughout the study will be recorded. Subjects must be questioned at each study visit concerning any new medications or changes in current medications including over-the-counter medication.

For each medication and non-study treatment, the following will be documented:

- Medication/treatment name (generic name may be used if trade name is unknown)
- Dose, unit, and frequency of dosing (individual dosages, not total daily dose).
 - **Note:** *Each new dose of medication should be recorded as a separate entry, with the exception of medications that are given on a sliding scale. For these, it is acceptable to enter the range of the dosage, including the start and stop dates for which the specified dosage range was used.*
- Route of dosing
- Indication for use
- The start date
- The stop date (if medication/therapy is not ongoing)

Please refer to Exclusion Criteria (Section 3.3.2) for a list of prohibited treatments and/or procedures. All other medications that are appropriate for the care of the subject may be

prescribed. If concomitant medications are started during the study, the indication for the concomitant medication should be considered an AE.

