3 STUDY DESIGN

This is a multi-center, two part study, designed to evaluate the efficacy, safety and tolerability of PRO 140 in conjunction with existing ART (failing regimen) for one week and Optimized Background Therapy (OBT) for 24 weeks respectively. The patient population for this trial are treatment-experienced patients with CCR5-tropic virus and demonstrates evidence of HIV-1 replication despite ongoing antiretroviral therapy with documented genotypic or phenotypic resistance to ART drugs within three classes, or two drug classes with limited treatment options.

The study is divided into four phases: Screening, Baseline, Treatment, and Follow-up.

Screening Phase begins with signing of Informed Consent and lasts up to 6 weeks. Subject will enter the Treatment Phase as soon as HIV-1 viral tropism, genotypic and/or phenotypic resistance results are available for review by Investigator.

The Baseline visit is to confirm HIV RNA continues to meet eligibility and will be conducted one week prior to the first treatment.

The Treatment phase is divided into two parts:

- **Part 1:** One-week treatment period consisting of PRO 140 along with existing ART (failed regimen).
- **Part 2:** 24-week treatment period consisting of PRO 140 along with Optimized Background Therapy (OBT)

All subjects will continue taking their existing ART (failed regimen) during the Screening Phase and first week of the Treatment Phase (Part 1). After Treatment Phase Part 1, all subjects will enter the 24-week treatment period (Part 2). During this period, all subjects will receive PRO 140 SC injection and OBT.

Study participants will be regularly monitored for viral load following initiation of PRO 140, and will cease weekly study treatment injections should they experience treatment failure.

Subjects who experience treatment failure at any point during Treatment Phase Part 2 will undergo the Treatment Failure (TF) Visit assessments and will be followed up every 4 weeks until viral suppression is achieved (i.e., plasma HIV-1 RNA levels below level of detection) or up to a maximum of 6 months after cessation of therapy if the treating physician does not feel that there is an antiretroviral regimen that will regain full viral suppression. Subjects who do not experience treatment failure, will be followed up every 2 weeks for a total of 4 weeks.

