7.11.14 Coagulation Indices

- Frequency of testing: At the Screening Visit, T12, EOT and TF.
- Prothrombin time (PT) and International Normalized Ratio (INR)

All laboratory reports will be reviewed by the Investigator.

Post-treatment abnormal results that are considered by the Investigator to be clinically significant will be recorded as adverse events. If the Investigator judges it necessary, testing may be repeated in order to make the determination of clinical significance. Validated, quality-controlled laboratory data will be transferred to the main database for analyses.

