9.1 ADVERSE EVENT

An adverse event (AE) is defined as any unfavorable or unintended sign, symptom, or disease that occurs or is reported by the subject to have occurred, or a worsening of a pre-existing condition. An AE may or may not be related to the study treatment.

AEs will be elicited through direct questioning and subject reports. Any abnormalities in visit evaluations, physical examination findings or laboratory results that the Investigator believes are clinically significant to the research subject and that occurred after initiation of the first study treatment will be reported as AEs. Abnormal findings that are NOT clinically significant (NCS) should not be recorded as an AE.

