9.1.1 Reporting of Adverse Events

Report initiation for all AEs and SAEs will begin at the time of the first treatment visit and continue up until the final study visit (i.e. up to NTF-FU2 for subject who do not experience virologic failure or until viral suppression is achieved for subjects who experience virologic failure). All events will be followed to resolution or until 30 days after the subject completes the study. A final assessment of outcome will be made at that time.

All AEs must be recorded in the subject's medical records and on the eCRFs. AEs will be reported using customary medical terminology along with the following information: the onset and end dates, whether the event is considered to be a SAE (see [Section 9.2](#)), the impact the event had on study treatment (see [Section 9.1.2](#)), the DAIDS AE grade (intensity) of the event (see [Section 9.1.3](#)), the causality of the event (see [Section 9.1.4](#)), whether treatment was given as a result of the event (see [Section 9.1.5](#)), and the outcome of the event (see [Section 9.1.6](#)).

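### Section 7.6 makes the indication of every newly started concomitant medicine an adverse event, contrary to Sections 9.1, 7.4 and 9.1.1, so some non-events can enter the AE listings and TEAE counts

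*Protocol*

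**What the plan says.** Section 7.6 has medicines recorded from 30 days before screening and throughout the study, each with its indication, start date and any stop date. It ends with the instruction "If concomitant medications are started during the study, the indication for the concomitant medication should be considered an AE". It makes no exception for preventive use, for stable conditions or for the period before dosing.

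Three other places set the limits of an AE:

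- Section 9.1: "An adverse event (AE) is defined as any unfavorable or unintended sign, symptom, or disease that occurs or is reported by the subject", extended to the worsening of a condition already present. The same section adds: "Abnormal findings that are NOT clinically significant (NCS) should not be recorded as an AE".
- Section 7.4: "Events that emerge prior to the first treatment (T1) will be recorded in the medical history and not as AEs".
- Section 9.1.1: "Report initiation for all AEs and SAEs will begin at the time of the first treatment visit". Every AE must then carry onset and end dates, a DAIDS grade, a causality assessment and an outcome.

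Section 8.7.5.1 counts an AE as treatment-emergent only if it begins no earlier than the first treatment. It tabulates TEAEs by system organ class, preferred term, severity grade and relationship.

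**The concern.** Section 7.6 is an instruction to sites on what to record, so the SAP cannot repair it later without re-adjudicating entries. Taken literally, it turns a medicine into an event even when nothing has happened to the subject.

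Such medicines are plausible here:

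- Exclusion 4 lets in subjects with a CD4 count below 200/mm³, and the HIV history in Section 7.5 asks about reactions to drugs for opportunistic-infection prophylaxis.
- Inclusion 9 requires two contraceptive methods and lists hormonal ones.
- Exclusion 7 bars vaccination only in the two weeks before first dose.

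Safety and tolerability belong to the primary objective, and Section 8.3 says the data are to supplement a licence application. With up to 40 centers and about 25 subjects, many sites would contribute very few subjects each. The AE counts would then partly reflect how literally each site read one sentence.

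**Working it through.** The protocol states no figure on this point, so there is none to reproduce. The check is to apply the rules side by side to four cases. Section 3 counts Screening and Baseline as phases of the study. In Table 4-1 the concomitant-medication row starts at the screening visit and the adverse-event row only at T1.

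| Medicine started | Under 7.6 | Under 9.1, 7.4 and 9.1.1 | TEAE under 8.7.5.1? |
|---|---|---|---|
| (a) Between consent and T1, for an event in that interval | AE | Medical history, not an AE | No, onset precedes first dose |
| (b) After T1, for a stable condition present before T1 | AE | Not an AE (no worsening) | No if the condition's own onset is entered; yes if the medicine's start date is used |
| (c) After T1, with no underlying condition (prophylaxis, contraception, vaccination) | AE | Not an AE | Yes; there is no other onset date to enter |
| (d) After T1, for a new or worsened condition | AE | AE | Yes, if dated to the new onset or worsening |

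The rules agree only in case (d). Case (a) is a contradiction in the text that does not reach the TEAE tables. Case (b) reaches them only through the wrong date, but Section 7.6 invites that error because the dates it collects are those of the medicine. Case (c) reaches them directly. It also requires a grade, a causality judgement and an outcome for something that has none of these.

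**Size per subject.** The planned number is up to 25 (Section 8.3). One subject is 1/25 = 0.04, or 4 percentage points, in any TEAE row where that subject would not otherwise appear. With N subjects the step is 100/N points.

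**Illustration for the any-TEAE row.** Let p be the share with a genuine TEAE, and q the share of the remaining subjects who gain one only through Section 7.6, taken as independent of p. Then

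share = p + (1 − p) × q.

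For p, take 28/40 = 0.70, the AE incidence that Section 1.4.2.7 reports for the earlier CD01 study. That was 350 mg monotherapy in suppressed patients, so it serves as a convenient anchor only. The protocol gives no value for q, so a range is shown:

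- q = 10%: 0.70 + 0.30 × 0.10 = 73%
- q = 20%: 0.70 + 0.30 × 0.20 = 76%
- q = 50%: 0.70 + 0.30 × 0.50 = 85%

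**The case against.** The best defence is that Section 9 governs. Its opening makes the investigator responsible for events that meet the AE definition, and a careful site would read Section 7.6 as a reminder to look for an event behind each new medicine. The study is single-arm, and Section 8.7.5 plans no inferential statistics for safety. This limits the consequence. It does not remove the contradiction, because Section 7.6 is unqualified and addresses the same staff.

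The defence is fully right against three larger readings that a reader might infer.

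- **That every subject acquires a false TEAE when OBT starts.** Section 3 does say "During this period, all subjects will receive PRO 140 SC injection and OBT". But Section 7.6 records antiretrovirals separately from all other medicines, and Table 4-1 lists OBT administration in a different row from concomitant medications. Even if OBT counted, its indication is HIV infection, whose onset precedes T1. A figure of 100% is not supported.
- **That the TEAE tables fill with pre-dose or pre-existing conditions.** The onset rule in Section 8.7.5.1 excludes them when they are dated correctly.
- **That each virologic failure becomes an AE discontinuation.** The closing paragraph of Section 7.11 reads: "Post-treatment abnormal results that are considered by the Investigator to be clinically significant will be recorded as adverse events". That depends on the investigator's judgement and is not automatic. Section 5.2.1 makes treatment failure its own reason to stop. The safety endpoint in Section 8.2.3 counts only treatment-related events, so an attribution to PRO 140 would also be needed. The 4-point step cannot be applied to that endpoint for each failure.

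**Conclusion.** Wrong as written, minor severity. Section 7.6 contradicts the AE definition in Section 9.1 and, for medicines started before T1, Sections 7.4 and 9.1.1. The practical effect is confined to cases (b) and (c): stable conditions dated by the medicine's start, and indications after first dose with no event behind them. These can enter the AE listings and the TEAE counts.

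How many would do so cannot be derived from the protocol. It depends on how literally sites apply the sentence and on which onset date they enter. The 4-point step assumes 25 treated subjects, and the 73% to 85% range rests on assumed values of q. The primary and secondary efficacy endpoints in Sections 8.2.1 and 8.2.2 do not depend on AE recording and are unaffected.

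**What to change.** Replace the last sentence of Section 7.6 with:

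*If a medication is started on or after first dose for a new or worsened condition that meets the AE definition in Section 9.1, that condition is recorded as an AE, dated by its own onset; prophylaxis, contraception, vaccination, unchanged pre-existing conditions and the planned start of OBT are not AEs in themselves.*

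Carry the same wording into any eCRF completion instructions. The clause on OBT settles a point that the present text leaves to inference.

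Do not go further and exempt HIV-1 RNA and CD4 results from AE recording. Exclusion 4 treats the CD4 count as a DAIDS-graded laboratory value, so a blanket exemption could remove gradable findings from the Grade 3 or 4 summary.

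The cost is one sentence, with no change to any visit, treatment or analysis. The small downside is that AE counts become slightly less comparable with any earlier study that used the same wording.
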